### 3.7.3 Analyses of Liver Biopsy Results

All endpoints will be summarized and analyzed based on the mITT population for MGL-3196 80 mg versus placebo. For liver biopsy, mITT includes only patients with both eligible baseline and Week 36 biopsies. Since this is for exploratory purpose, no multiplicity will be controlled.

Responder variables at Week 36 include:

- NASH Biopsy Responders:
  - The number and percentage of patients achieving a 1-point reduction in NAS;
  - the number and percentage of patients achieving a 2-point reduction in NAS at 36 weeks;
  - the number and percentage of patients achieving a 2-point reduction in NAS at 36 weeks; and either  $\geq 1$  point reduction in lobular inflammation or  $\geq 1$  point reduction in hepatocellular ballooning; and
  - the number and percentage of patients achieving a 2-point reduction in NAS at 36 weeks; and no worsening of fibrosis.
- NASH Component Responder definition (only requires one or more criteria):
  - reduction in hepatocellular steatosis; or
  - reduction in lobular inflammation; or
  - reduction in hepatocellular ballooning.
- Fibrosis Responders:
  - the number and percentage of patients achieving  $\geq 1$  stage reduction in fibrosis;
  - the number and percentage of patients achieving  $\geq 1$  stage reduction in fibrosis; and no worsening of NAS; and
  - the number and percentage of patients achieving  $\geq 2$  stage reduction in fibrosis.
- NASH Resolution Responder Definition (requires both criteria):
  - lobular inflammation = 0 or 1; and
  - hepatocellular ballooning = 0.

- NASH Resolution Responders with at least a 2-point reduction in NAS at Week 36.
- Other exploratory NASH Resolution Responders:

- The number and percentage of patients achieving a change in NASH diagnosis (ie, from definite NASH to not-NASH based on histology) from baseline to Week 36.

The definite NASH based on histology is specified as: fibrosis stage 1 to 3 and a NAS of  $\geq 4$  with at least a score of 1 in each of the following NAS components:

- Steatosis (scored 0 to 3),
- Ballooning degeneration (scored 0 to 2), and
- Lobular inflammation (scored 0 to 3).

Fisher's exact test will be used to compare the percentages between MGL-3196 80 mg versus placebo. Confidence intervals and p-values will also be provided.

NOTE:

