- The analyses performed on the NASH Resolutions endpoint will exclude patients with  $>9.5\%$  weight loss from Screening to Week 36 (the percent change in body weight from Screening to Week 36 is  $>-9.5\%$ ), including the patients only as secondary analyses. Conversely, other liver biopsy and study endpoints will include the patients, excluding them only as secondary analyses.

Other liver biopsy variables include:

- The change in fibrosis stage from baseline at 36 weeks; as a continuous variable and descriptively by numbers and percentages of patients in which fibrosis stage improved, was unchanged or worsened, for exploratory purposes only
- The change in portal inflammation from baseline at 36 weeks; and
- The change in parameters of NASH liver biopsy (NAS) from baseline at 36 weeks. The NAS score will also be summarized descriptively as a continuous variable for exploratory purposes only.
- Correlation of reduction of liver fat on MRI-PDFF at 12 and 36 weeks with improvement or resolution of NASH on liver biopsy.

Analyses of liver biopsy data will be performed on the mITT population for the following subgroups:

- Week 36 SHBG group ( $\geq 88\%$ ,  $<88\%$  change from baseline to mean SHBG post Week 12 through Week 36);
- Exposure group (AUC  $<2700$  ng\*hr/mL, AUC  $\geq 2700$  ng\*hr/mL);
- Baseline Fibrosis Stage 2/3;

- Weight loss from Screening to Week 36 (<5% weight loss,  $\geq 5\%$  weight loss,  $< 7\%$  weight loss,  $\geq 7\%$  weight loss,  $> 9.5\%$  weight loss);
- Baseline MRI-PDFF  $\geq 20\%$ ;
- Gender (male, female);
- Ethnicity (Hispanic or Latino, Not Hispanic or Latino );
- Stage of NASH ( $\geq 5$ ,  $< 5$ );
- PNPLA3 SNP phenotype (Homozygous, Heterozygous, negative);
- Type 2 diabetes (yes or no);
- MGL-3196 treated patients who have 30% or more reduction in hepatic fat fraction by MRI-PDFF from baseline at Week 12 and 36, that is, the percent change from baseline to Week 12 and 36 is  $\leq -30\%$  versus all Placebo treated patients;
- MGL-3196 treated patients who have 5% or more absolute reduction in hepatic fat fraction by MRI-PDFF from baseline at Week 36, that is, the change from baseline to Week 12 is  $\leq -5\%$  in hepatic fat versus all Placebo treated patients;
- MGL-3196 treated patients who have 5% or less hepatic fat fraction by MRI-PDFF at Week 12 and 36, that is, the hepatic fat fraction measurement at Week 12 and 36 is  $\leq 5\%$  versus all Placebo treated patients; and

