### 3.7.4.4 Fibrosis Markers

Fibrosis markers will be assessed by visits based on ITT population. Change and percent change from baseline to Week 12 and Week 36 endpoints will be summarized. The same ANCOVA model will be used for analyzing the change and percent change from baseline to

Week 12 and to Week 36 for fibrosis markers, by overall treatment group, exposure group, and SHBG groups.

Summary and analysis of fibrosis markers will be repeated on all ITT population with Week 12 liver fat reduction  $\geq 30\%$  from baseline in MRI-PDFF for active treatment group vs. all placebo subjects. In addition, the following subgroups will be explored at both Week 12 and Week 36 for each corresponding fibrosis marker:

- Week 12 SHBG group ( $\geq 75\%$ ,  $< 75\%$  change from baseline to Week 12) for men and women separately;
- Week 36 SHBG group ( $\geq 88\%$ ,  $< 88\%$  change from baseline to mean SHBG post Week 12 through Week 36);
- Exposure group (AUC  $< 2700$  ng\*hr/mL, AUC  $\geq 2700$  ng\*hr/mL);
- Baseline ELF  $\geq 9$ ;
- Baseline PIIINP  $\geq 8$   $\mu\text{g}/\text{L}$ ;
- Baseline TIMP  $\geq 129$   $\mu\text{g}/\text{L}$ ;
- Baseline HA  $\geq 50$   $\mu\text{g}/\text{L}$ ; and
- Baseline PRO-C3  $\geq 10$   $\mu\text{g}/\text{L}$ , and  $\geq 17.5$   $\mu\text{g}/\text{L}$ .

For the fibrosis markers (e.g. ELF, pro-C3, adiponectin and CK-18), change from Week 12 to Week 36 will also be summarized and analyzed. This will show durability of response and whether the biomarkers at week 12 is a good a predictor of response or Week 36 is better, and also provide the significance between drug treated and placebo in the change in non-invasive biomarker parameters between Week 12 and Week 36. If there is a significant decrease in ELF and components in the whole population between Weeks 12 and 36 that is larger than the decrease between baseline and Week 12, it might suggest that differences between Week 12 to Week 36 and Week 0 to Week 36 of fibrosis marker data may be used to predict response on liver biopsy.

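### Three exploratory biopsy subgroup analyses and one repeat fibrosis-marker analysis set drug patients chosen for their MRI-PDFF response against all placebo patients, which favours the drug whenever fat change and the outcome are correlated

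*SAP*

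**What the plan says.** SAP 3.7.3 begins with the main biopsy analysis: "All endpoints will be summarized and analyzed based on the mITT population for MGL-3196 80 mg versus placebo". For this section, mITT means patients with an eligible biopsy at both baseline and Week 36. Fisher's "exact test will be used to compare the percentages between MGL-3196 80 mg versus placebo", and confidence intervals and p-values are to be given. The section adds: "Since this is for exploratory purpose, no multiplicity will be controlled".

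The subgroup list that follows has 13 named entries and a final one for data-driven groups. Three entries define the drug group by an MRI-PDFF result:

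- "MGL-3196 treated patients who have 30% or more reduction in hepatic fat fraction by MRI-PDFF from baseline at Week 12 and 36";
- drug patients with an absolute fall of 5 points or more;
- drug patients whose fat fraction is 5% or less.

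Each is compared "versus all Placebo treated patients".

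SAP 3.7.4.4 repeats the fibrosis-marker analysis in patients with a Week 12 fall of at least 30% "from baseline in MRI-PDFF for active treatment group vs. all placebo subjects". The parent section, 3.7.4, carries the same exploratory label.

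The SAP also plans to study the link directly: "Correlation of reduction of liver fat on MRI-PDFF at 12 and 36 weeks with improvement or resolution of NASH on liver biopsy". Section 3.7.5 says its correlations are run for the two arms separately.

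**The concern.** Response on MRI-PDFF is an efficacy outcome seen after randomisation. In these four analyses it filters one arm only. Drug patients whose fat did not fall are removed, while placebo patients stay in whether their fat fell or not. Randomisation no longer makes the two sets comparable.

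If patients whose fat falls also tend to improve on biopsy, with or without drug, the filtered drug group does better even when the drug does nothing for histology. For some endpoints part of that link is built in. Steatosis is scored within NAS, and "reduction in hepatocellular steatosis; or" is on its own enough to make a patient a component responder. For NASH resolution (ballooning and inflammation only), fibrosis stage and serum markers, a link is plausible but the documents do not establish one.

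Such a table would be read as showing that the drug improves NASH in patients whose liver fat falls. The contrast cannot show that, because it mixes any drug effect with selection.

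**Working it through.** **Plan's own figures.** The SAP states no operating characteristic for these contrasts. The nearest figure is the primary power in SAP section 4: difference 30 points, SD 35, 36 per group, alpha 0.025, stated as 90%. A two-sided two-sample t-test gives 90.8%, so the SD and effect can be borrowed.

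**Inputs from the documents.** SD of percent fat change is 35; planned difference is −30; the selection rule is a change of −30% or lower. There are 36 placebo completers and, at 2:1, 2 × 36 = 72 drug patients. (The protocol's Amendment 6 tables show 38 and 78 with MRI-PDFF; the biopsy-evaluable numbers are not given.)

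**Assumed, because the documents give no usable value.** Biopsy response is 30% in both arms (no histology effect). Mean placebo fat change is −10% or 0. Within-arm correlation ρ between fat reduction and a latent normal histology score is 0 to 0.7. The 30% rule is applied at one visit. The Fisher test is two-sided at 0.05.

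**Step 1: share selected.** With mean drug-arm change m, c = (−30 − m)/35 and the share is Φ(c).

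- Fat-lowering drug, placebo −10: m = −40, c = 10/35 = 0.286, share 61%.
- Fat-lowering drug, placebo 0: m = −30, c = 0, share 50%.
- Inert drug, both arms −10: m = −10, c = −20/35 = −0.571, share 28%.

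**Step 2: apparent response among those selected.** With standardised fat change Z and latent histology score Y, this is P(Y > z₀.₇₀ | Z ≤ c), where Y has correlation ρ with −Z. The true rate in both arms is 30%.

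| Setting | ρ = 0.3 | ρ = 0.5 | ρ = 0.7 |
|---|---|---|---|
| Lowers fat only, placebo −10 | 36% | 41% | 45% |
| Lowers fat only, placebo 0 | 38% | 44% | 51% |
| Inert drug, both arms −10 | 43% | 53% | 65% |

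**Step 3: how often Fisher's test declares a difference** (6,000 simulated trials per setting; repeat runs agree to within about 2 points).

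| Setting | ρ = 0.3 | ρ = 0.5 | ρ = 0.7 |
|---|---|---|---|
| Lowers fat only, placebo −10 | 7% | 14% | 25% |
| Lowers fat only, placebo 0 | 9% | 20% | 37% |
| Inert drug, both arms −10 | 13% | 35% | 67% |

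At ρ = 0 there is no inflation in any setting. Fisher's test on the full arms stays near 4% throughout.

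**Step 4: a continuous marker.** Selection shifts the mean by ρ·φ(c)/Φ(c) SD. At c = 0 this is 0.80ρ, or 0.24 SD at ρ = 0.3 and 0.40 SD at ρ = 0.5. With 78 and 38 patients and a t-test standing in for the planned ANCOVA, a drug that lowers fat only (placebo change 0) gives a significant result in its own favour in 18% and 44% of trials, against a nominal 2.5%.

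**Step 5: is filtering both arms a remedy?** If the drug lowers fat, comparing drug responders with placebo responders gives a rate in favour of drug of 0.1% to 0.9%, below the nominal 2.5%. That contrast is biased against the drug, so it is not a substitute.

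**The case against.** The strongest reply is about place and status. The whole-arm comparison comes first and covers every biopsy endpoint. The disputed contrasts are three of 13 named subgroups and one repeated marker analysis, all in sections labelled exploratory. Within-arm correlations of fat change with biopsy outcome are already planned in 3.7.5. All of this stands, and it limits how much weight the point can carry. But the exploratory label waives multiplicity control only. Selection bias sits in the estimate, and no alpha adjustment removes it. Nothing in the SAP marks these contrasts as non-randomised or exempts them from the section's tests and p-values.

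Three stronger readings are tempting and go too far:

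- A reader might infer that the contrasts are positive by construction. At zero correlation there is no inflation, and a built-in link exists only where steatosis enters the endpoint. With an active drug the contrast mixes effect and selection; it is not pure artefact.
- A reader might say that the better half of the drug arm is used. Responder shares are redacted; the share is 28% to 61% under the assumptions here.
- A reader might take the inert-drug figures as the expected size. The protocol's Amendment 6 rationale reports that the Week 12 MRI-PDFF endpoint was met, so a drug that lowers fat but not histology is the relevant case, and its figures are smaller.

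The simulation is also narrow: one rule, one visit, one binary endpoint. If the 30% rule must be met at both visits (assumed between-visit correlation 0.7), the inert-drug rates are still about 12% and 32% at ρ of 0.3 and 0.5. The 5-point and 5%-or-less rules were not simulated.

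**Conclusion.** The point holds for these four analyses and no further. One-sided selection on a post-randomisation response biases them towards the drug whenever fat change and the outcome are positively correlated within an arm. For a drug that lowers fat by the planned 30 points and leaves histology unchanged, the chance of a declared difference is about 7–9%, 14–20% and 25–37% at correlation 0.3, 0.5 and 0.7; the ranges reflect a placebo fat change of −10% to 0.

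These sizes rest on assumed correlation, response rate, mean fat change and biopsy numbers. The direction of the bias needs only a positive correlation. The documents do not support the inference that the biopsy endpoints as a whole are tested this way, or that the primary MRI-PDFF result is touched. The change should be made, but the study's main conclusions do not depend on it.

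**What to change.** In SAP 3.7.3 and 3.7.4.4, replace the four contrasts with tables of histology and markers by MRI-PDFF response (yes/no) within each arm, placed beside the correlations already planned in 3.7.5. Label them as non-randomised association. State that the drug-versus-placebo Fisher test, ANCOVA, p-values and confidence intervals do not apply to sets chosen by MRI-PDFF response. Merely deleting the all-placebo phrase is not enough, because the entries would then fall under the section's general drug-versus-placebo rule. State also that conclusions about drug effect rest on the whole-arm comparison.

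If the listed contrast is kept because it was prespecified, show it descriptively, with that caveat and no p-value.

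While editing, say whether the 30% rule must be met at both visits or at each separately, and reconcile the absolute-fall entry, which names Week 36 and then defines the change at Week 12.

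The cost is small table changes and the loss of a favourable-looking comparison. If the treatment code had already been revealed when the change is made, record it as a deviation in the study report.

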### 3.7.4 Analyses of Other Efficacy Endpoints

Summary statistics (number of patients, mean, standard deviation, median, minimum, and maximum) for all visits, including the change from baseline and percent change from baseline, will be provided for each parameter for the mITT population.

The parameters will be analysed based on the mITT population. For certain efficacy endpoints, such as liver enzymes at Week 12, analysis will be repeated on MRI population as well. Since this is for exploratory purpose, no multiplicity will be controlled. Where stated, the last observation carried forward will be used for missing value imputation when applying an ANCOVA model.

#### 3.7.4.1 Liver Enzyme (ALT, AST, and GGT)

The same ANCOVA model for the percent change and change in hepatic fat fraction will be used for analyzing the percent change and change from baseline to Week 12 in ALT, AST, and GGT. That is, the percent change and change from baseline to Week 12 in ALT or AST will be analyzed with the ANCOVA model with treatment as a factor. Baseline ALT, AST, or GGT value will be a covariate in the change from baseline analysis. A pairwise comparison will be

performed between MGL-3196 active and placebo. LS means for the treatment difference, 95% confidence interval and p-value will be provided.

These analyses will be repeated at the Week 30, Week 36 and Week 38 time points for the mITT population. From the results of Week 36 and 38, the sustainability of drug effect will be evaluated.

Moreover, the analyses will also be repeated for the following derived values:

- The lowest ALT, AST, or GGT endpoint value from Week 30 and Week 36. If a patient terminated early, the lowest value from the early termination visit and the previously scheduled visit will be considered the lowest value; and
- The lowest ALT, AST, or GGT value after Week 12 and through Week 36.

Unscheduled visits will not be included in these derivations.

Analyses of ALT will be repeated for females with baseline ALT  $\geq 30$  U/L and males with baseline ALT  $\geq 45$  U/L.

The Mixed Model for Repeated Measurements (MMRM) will be used to test the robustness of the results of treatment comparison at each visit. The treatment difference will be estimated from the model for Weeks 12, 30 and 36.

Analyses of ALT, AST, and GTT may be performed for the following subgroups:

- Week 12 SHBG group ( $\geq 75\%$ ,  $< 75\%$  change from baseline to Week 12) for men and women separately;
- Week 36 SHBG group ( $\geq 88\%$ ,  $< 88\%$  change from baseline to mean SHBG post Week 12 through Week 36);
- Exposure group (AUC  $< 2700$  ng\*hr/mL, AUC  $\geq 2700$  ng\*hr/mL);
- Females with baseline ALT  $\geq 30$  U/L and males with baseline ALT  $\geq 45$  U/L; and
- Any other data driven groups.

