9.8 Clinical Laboratory Evaluations

All standard blood and urine tests will be performed by a central laboratory. For the purposes of this study, fasting will be defined as nothing by mouth except water for 10 hours. If the patient is not fasting, the Investigator will reschedule the visit as soon as possible but no later than 3 days. Laboratory certification (including expiration date) and normal reference ranges for all laboratories used during the study will be on file with [REDACTED] prior to study initiation. For a complete list of laboratory assessments that will be performed, see Appendix C. For blood sampling procedures, including information on blood volume, collection tubes, sample processing, storage, and shipping, see the Laboratory Manual for this study.

The Investigator must review and sign all laboratory test reports. The Investigator will be notified if laboratory values are outside of normal range and notified of alert values. In this case, the Investigator will be required to conduct clinically appropriate follow-up procedures.

The following analytes will be measured at the Screening Visit (Week -6 to 0), Baseline Visit (Day 1), Main Study Weeks 2, 4, 8, 12, 16, 20, 24, 30, 36 and 38, and the Early Termination Visit, and Extension Study Day 1, Extension Study Weeks 2, 4, 8, 12, 16, 20, 24, 28, 32, 36, and 38, and the Extension Study Early Termination Visit:

- Chemistry – ALP, ALT, amylase, AST, blood urea nitrogen, calcium, carbon dioxide, chloride, creatine kinase, creatinine, direct bilirubin, eGFR (derived from creatinine), [REDACTED] lactate dehydrogenase, lipase, magnesium, phosphate, potassium, serum albumin, sodium, total bilirubin, total protein, and uric acid; and
- Hematology – hemoglobin, hematocrit, red blood cell count, white blood cell count, platelets, mean corpuscular volume, mean corpuscular hemoglobin, and mean corpuscular hemoglobin concentration, red blood cell morphology, % differentials, and absolute differentials.

The following urinalysis analytes will be measured at the Screening Visit (Week -6 to 0), Baseline Visit (Day 1), Main Study Weeks 2, 4, 8, 12, 16, 20, 24, 30, and 36, and the Early Termination Visit, and Extension Study Day 1, Extension Study Weeks 2, 4, 8, 12, 16, 20, 24, 28, 32, 36, and 38, and the Extension Study Early Termination Visit: pH, specific gravity, protein, glucose, ketones, bilirubin, blood, nitrate, urobilinogen, and leukocyte esterase.

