### 3.7.4.2 Lipid Measurements

All lipid measurements will be summarized by visit, as well as absolute and percent change from baseline to each post-baseline visit.

The same ANCOVA model as primary efficacy analysis will be used for analyzing the percent change and change:

- From baseline to Week 4,
- From baseline to Week 12 with LOCF (after Day 1 and up to Week 12),
- From baseline to Week 30 with LOCF (after Week 12 and up to Week 30),
- From baseline to Week 36 with LOCF (after Week 12 and up to Week 36),
- Average between Week 30 and Week 36, and
- Average between Week 16 and Week 36

for direct LDL-C, triglycerides, Lp(a), HDL, Non-HDL, Total Cholesterol, Apo C-III (after Week 12 only), and Apo B.

Lp(a) will be analyzed separately for baseline value  $\leq 10$  nmol/L and baseline value  $> 10$  nmol/L. In the ANCOVA model for change from baseline, baseline value will be included as a covariate. But the covariate of baseline value will not be included in the model for the analysis of percent change from baseline.

If skewness from normality is observed for triglycerides data, then the triglycerides value will be logarithm-transformed before fitting the ANCOVA model. The treatment difference between two visits will then be transformed back as the percent change from. If the normality assumption still can't be satisfied with the logarithm-transformed data, a non-parametric approach (Wilcoxon rank-sum test) will be used to compare the difference in median TG change or percent change between treatment groups.

A logistic regression model with treatment as a factor and baseline as a covariate may be used to compare the percentages of patients who achieve a change from baseline to endpoint in Lp(a) ( $\leq 10$  nmol/L vs.  $> 10$  nmol/L) between the MGL-3196 dose versus placebo. The odds ratio, confidence interval, and p-value will be provided.

Analyses of lipids may be performed for the following subgroups:

- Week 12 SHBG group ( $\geq 75\%$ ,  $< 75\%$  change from baseline to Week 12) for men and women separately;
- Week 36 SHBG group ( $\geq 88\%$ ,  $< 88\%$  change from baseline to mean SHBG post Week 12 through Week 36);
- Exposure group (AUC  $< 2700$  ng\*hr/mL, AUC  $\geq 2700$  ng\*hr/mL);
- Baseline Direct LDL Category ( $< 100$  mg/dL,  $\geq 100$  mg/dL);
- Baseline Triglycerides Category ( $\leq 150$  mg/dL,  $> 150$  mg/dL); and
- Any other data driven groups.

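### Two supplementary liver-enzyme analyses take the lowest of several visits, which builds a fall from baseline into both arms; the mean over the same visits avoids this

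*SAP*

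**What the plan says.** SAP Section 3.7.4.1 analyses ALT, AST and GGT by ANCOVA at Weeks 12, 30, 36 and 38. Baseline is a covariate for change but not for percent change. The section names a between-arm comparison: "LS means for the treatment difference, 95% confidence interval and p-value will be provided". An MMRM "will be used to test the robustness of the results of treatment comparison at each visit".

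The same analyses are then repeated on two derived values:

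- "The lowest ALT, AST, or GGT endpoint value from Week 30 and Week 36". For patients who stop early, "the lowest value from the early termination visit and the previously scheduled visit will be considered the lowest value".
- "The lowest ALT, AST, or GGT value after Week 12 and through Week 36". No early-termination rule and no minimum number of values is given here.

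The section adds: "Unscheduled visits will not be included in these derivations". Protocol Section 9.8 schedules chemistry at "Main Study Weeks 2, 4, 8, 12, 16, 20, 24, 30, 36 and 38", so the second value is the lowest of up to five (Weeks 16, 20, 24, 30 and 36). Under SAP Section 3.1 the baseline is one Day 1 measurement. SAP Section 3.7.4 labels this group of analyses exploratory, without multiplicity control.

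For lipids, SAP Section 3.7.4.2 uses means over the same two windows, including "Average between Week 16 and Week 36". Inclusion criterion 9 (Protocol Section 4.1) also averages ALT over Weeks 16 to 30 to decide extension eligibility.

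**The concern.** The minimum of several noisy readings lies below a patient's true level, and the gap widens as more readings are taken. Setting that minimum against one unselected baseline reading produces a fall in both arms even when nothing has changed.

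This matters mainly for within-arm claims. The Week 12 enzyme tables in the protocol's Amendment 6 summary give each arm's change with a CI and p-value, and their captions describe falls within the treated group as significant. If that layout is reused for the lowest values, a significant fall is close to guaranteed for the five-visit version in any arm, placebo included.

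A second issue is that the size of the artefact depends on how many values a patient contributes. If that number differs by arm, the treatment difference is biased as well.

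**Working it through.** The documents give no figure for these enzyme analyses, so there is none to reproduce. The sample-size section covers MRI-PDFF only.

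**Inputs from the documents.** Five or two post-baseline values; one baseline value; 39 placebo and 79 MGL-3196 patients (mITT tables in the Amendment 6 summary); the SAP models (treatment only for percent change, treatment plus baseline for change).

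**Assumptions not in the documents.** Within-patient CV 10 to 30%, independent visit errors, mean ALT 60 U/L, between-patient CV 45%, lasting patient-level change with CV 20%.

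**Step 1: expected minimum.** For k independent normal errors with SD σ, the mean of the minimum is ∫ x·k·φ(x)·[1−Φ(x)]^(k−1) dx, in units of σ.

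| k | Mean of minimum | Variance of minimum | Variance of mean |
|---|---|---|---|
| 2 | −0.564 | 0.682 | 0.500 |
| 5 | −1.163 | 0.447 | 0.200 |

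At a CV of 20%, the five-visit shift is 1.163 × 20 = 23% of the true level.

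**Step 2: simple within-arm test, n = 39, no true change.** The change has variance (1 + Var of minimum + τ²)σ², where τ is the SD of lasting patient-level change in units of σ.

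- Five visits, τ = 0: 1.163 / √(1.447/39) = 6.0. With τ = 1 it is 4.6, and with τ = 2 it is 3.1.
- Two visits, τ = 0: 0.564 / √(1.682/39) = 2.7. With τ = 1: 0.564 / √(2.682/39) = 2.2. With τ = 2: 0.564 / √(5.682/39) = 1.5.

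Against a critical value of about 2, the five-visit minimum is significant on average throughout. The two-visit minimum is borderline.

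**Step 3: simulation of the SAP models, lognormal error, no true change.** Placebo, lowest-of-five, percent change:

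| Visit CV | Mean change | Significant fall |
|---|---|---|
| 10% | −10.4% | 86% |
| 15% | −14.6% | 96% |
| 20% | −18.2% | 98% |
| 25% | −21.6% | 99% |
| 30% | −24.4% | 99% |

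In the change analysis the placebo LS mean for lowest-of-five is −7 to −18 U/L, significant in 86 to 100% of trials. The mean of the same visits gives about 0 U/L and a significant fall in 2 to 3%.

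For lowest-of-two, percent change is −4.7 to −8.9%, significant in 26 to 34%. The change analysis rejects more often, in about 60% at CV 20%. Over both analyses and the CV range the figure is roughly 30 to 80%.

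**Step 4: between-arm comparison.**

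- Equal visit counts, no effect: the lowest-value test rejects in 4.4 to 5.9% of trials, so its size is kept.
- True 15% effect, change analysis, CV 15, 20 and 30%: power is 82, 72 and 56% for lowest-of-five against 84, 77 and 61% for the mean.
- Why power falls, at CV 20%: the effect shrinks from −9.0 to −7.1 U/L while the SD of the difference falls from 3.58 to 2.98. The ratios are 9.0/3.58 = 2.51 and 7.1/2.98 = 2.38.
- Unequal counts, no effect, three placebo against five active values, CV 20%: false difference of −5.4 percentage points and 17.5% rejections, against 5.0% for the mean.

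**The case against.** The strongest defence is that these are two exploratory additions. The protocol defines the enzyme variable as change at Weeks 12 and 36, and the SAP analyses it with single-visit ANCOVA and MMRM, which involve no minimum. The inference that the SAP names is between arms, placebo passes through the same rule, and with matching visit counts the test is valid under no effect. With a true effect the minimum understates the difference. All of this stands.

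The within-arm p-values appear in Week 12 tables, none of which uses a lowest value. That also stands: the within-arm problem is conditional on the same layout being reused.

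A reader might infer that early terminators get two values while completers get five. The text does not say so. The two-value rule belongs to the Week 30/36 endpoint, where completers also have two. For the five-visit endpoint, counts can differ through missed visits or withdrawal, but nothing in the documents shows that they differ by arm. A mild imbalance does little: if 10% of one arm had two values and everyone else five, the bias is 0.10 × (1.163 − 0.564) = 0.06 within-patient SD.

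A reader might also infer that the mean always has the smaller standard error. That holds for additive error (visit-error variance 0.200 against 0.447) but reverses under proportional error. The general advantage is in power, and it is modest.

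**Conclusion.** The point holds for the two lowest-value analyses only, and mainly for within-arm reporting. If within-arm p-values are given, a placebo arm with no change would show a significant fall in about 86 to 100% of trials for lowest-of-five and roughly 30 to 80% for lowest-of-two. The documents do not support saying that the enzyme results as a whole are artefacts, or that the planned between-arm test is invalid. That test loses about 1 to 7 points of power with a 15% effect, and is biased only if visit counts differ by arm; three against five is an extreme case.

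The percentages rest on the assumed CVs and on independent visit errors. Correlated errors between visits would reduce the artefact. The direction of the bias, and its growth with the number of visits, do not depend on the assumed CV.

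The change is worth making: the SAP already uses the better summary for lipids and the cost is small. It does not decide the trial's conclusions.

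**What to change.** In SAP Section 3.7.4.1, replace the two lowest-value analyses with the mean of Weeks 30 and 36 and the mean of Weeks 16 to 36, matching Section 3.7.4.2. Keep baseline as the covariate in the change analysis. If a lowest value is retained, present it descriptively, without a within-arm p-value.

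The cost is SAP wording and the matching table shells. The downside for the sponsor is that within-arm falls will look smaller.

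The mean removes only the selection of the minimum. Regression to the mean remains in the subgroup chosen for high baseline ALT: about −1.6 U/L in simulation with an illustrative cut of 40 U/L at CV 20%. Percent change still drifts upward, by about 1 to 9% at CV 10 to 30%, because one noisy baseline is the denominator. Both are further reasons to rest conclusions on the between-arm difference.
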